4.5.3 Exploratory Efficacy Endpoints

The MS guideline of the European Medicines Agency ([EMA, 26 March 2015](#)) suggests a number of primary and secondary efficacy outcome measures. On the basis of these recommendations, the following exploratory efficacy outcomes will be analyzed:

- MRI derived parameters: number of gadolinium-enhancing T1 lesions and number of new or enlarging T2 lesions. For the combined ECP and OLE periods, these parameters will be analyzed by scheduled visit as follows:
 - Negative binomial model adjusted by Geographical Region (US vs. ROW) and Age (≤ 45 , > 45 years) for the baseline visit.

- Negative binomial model adjusted by Baseline T1 Gd Lesion (present or not) or Baseline T2 lesion count, Geographical Region (US vs. ROW) and Age (≤ 45 , >45 years) for the post-baseline visits.
- If the negative binomial model doesn't converge due to small number of lesion counts, unadjusted rate and exact poisson CI will be presented.
- Cognitive impairment: change from baseline to Week 120 in the Paced Auditory Serial Addition Test (PASAT).
- Percent change from baseline to Week 120 in total brain volume, white matter volume and cortical gray matter brain volume and the percent change from Week 24 to Week 120 in white matter volume and grey matter brain volume. For all parameters, analyses will be extended to include data collected during the OLE period where percentage change from Week 24, baseline and OLE baseline until the last mature visit will be analyzed.

Additional exploratory outcomes that will be analyzed include the following:

- Proportion of patients with CDP at Week 120
- Functional impairment: change from baseline in EDSS score, and change from baseline in MSFCS. For both parameters, analyses will be extended to include data collected during the ECP and OLE periods. Change from baseline during ECP, change from baseline until the last mature visit during the combined ECP+OLE periods and change from OLE baseline until the last mature visit during the OLE period will be analyzed.
- The change in fatigue, as measured by the Modified Fatigue Impact Scale (MFIS) total score and subscale scores (Physical impact, Cognitive impact, and Psychological impact) from baseline to Week 120. Additional data from the OLE period will be descriptively analyzed.
- The change in quality of life, as measured by the SF-36v2 MCS score from baseline to Week 120. Additional data from the OLE period will be descriptively analyzed.
- Time to composite confirmed disability progression (cCDP) over the treatment period, defined as an increase in EDSS that is sustained for at least 12 weeks (0.5 or 1, same criteria as for the primary endpoint time to 12-week CDP) or a 20 percent increase in 25-foot timed walk that is sustained for at least 12 weeks or a 20 percent increase in 9-hole peg test that is sustained for at least 12 weeks. This analysis will be repeated to include the EDSS assessments performed during the ECP and OLE periods for ECP and the combined DB+OLE periods, with the same baseline as for the analysis during DB. Analysis containing only data from OLE will be performed considering the OLE baseline.

Additional endpoints for the extension periods:

- Change from baseline in non-enhancing T1 lesion volume will be analyzed similarly to the T2 lesion volume. Ratio relative to baseline until the last mature visit during the combined ECP+OLE period and ratio relative to OLE baseline until the last mature visit during the OLE period will be analyzed.

- Time to Onset of CDP confirmed for ≥ 48 weeks

Time to onset of CDP will be analyzed with use of a 48 week confirmation window for disability progression. The analysis will be conducted as described for the primary analysis, with the exception that the time to onset of CDP (48 week confirmation) is defined as the time from baseline to the first disability progression that is confirmed at the next regularly scheduled visit ≥ 48 weeks (≥ 329 days) after the initial disability progression.

The analysis will be performed for ECP and the combined DB+OLE periods, with the same baseline as for the analysis during DB. Analysis containing only data from OLE will be performed considering the OLE baseline.

- Time to Onset of cCDP for at least 24 weeks or 48 weeks

Time to onset of cCDP will be analyzed with use of a 24 or 48 week confirmation window for disability progression. The analysis will be conducted as described for the primary analysis.

The analyses will be performed for ECP and the combined DB+OLE periods, with the same baseline as for the analysis during DB. Analysis containing only data from OLE will be performed considering the OLE baseline.

- Time to Onset of Confirmed EDSS ≥ 7 for at least 24 weeks or 48 weeks

Time to onset of confirmed EDSS ≥ 7 will be analyzed with EDSS ≥ 7 (requiring wheelchair) to be defined as a disability progression event that is sustained for at least 24 or 48 weeks. The analysis will be conducted as described for the primary analysis.

The analyses will be performed for ECP and the combined DB+OLE periods, with the same baseline as for the analysis during DB. Analysis containing only data from OLE will be performed considering the OLE baseline.

- Annualized Percentage Change in MRI assessments from Baseline during the combined ECP and OLE Periods

Due to the event driven study design and no additional MRI assessments were performed between 120 weeks and OLE start, the time gap between 120 weeks and OLE start varies from patient to patient. Hence, an annualized change in all MRI assessments, including the total brain volume, white matter volume, cortical gray matter volume, T1 lesion volume and T2 lesion volume is analyzed for the combined ECP and OLE periods, which takes into account the variable time difference between visits for each patient.

At each scheduled visit during the ECP and OLE periods, calculate the annualized change from the previous visit as follows:

$$CHG = \frac{\frac{AVAL - lag(AVAL)}{lag(AVAL)} \times 100}{(ADT - lag(ADT))/365.25}$$

where AVAL corresponds to the MRI value at the current visit, and ADT corresponds to the date of the current visit.

For T1 and T2 lesion volume, the log transformation is applied, and 0 values are imputed to 0.009

$$LOGCHG = \frac{\log(AVAL) - \log(lag(AVAL))}{(ADT - lag(ADT))/365.25}$$

The OLE MRI assessments are backdated as follows:

- Create an SoA from Week 120 with a visit every 48 weeks, e.g., Week 168, Week 216, etc
- All OLE visits prior to Week 168 will be assigned to Week 168 ≥ New visit label
- For all remaining OLE visits, they will be assigned to the nearest Week xxx with a time window of ±24 weeks ≥ New visit label
- Use the new visit labels (no OLE Week yy visit label) for the analysis
- If multiple OLE visits are windowed to the same Week xxx visit, then the latest chronological visit will be used for the analyses
- Neurofilament Light chain (NfL) data collected during the ECP and OLE periods will be summarized descriptively. Summary statistics of the absolute NfL values will be presented at all scheduled visits along with the percentage change from baseline. A corresponding plot will be produced. The analyses will be performed for the ECP period only as well as for the combined ECP and OLE periods.

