- ^g **Vital signs** will be obtained while the participant is in the semi-supine position (after 5 minutes), including pulse rate, systolic and diastolic blood pressure, respiration rate, and temperature. At infusion visits, the vital signs for all participants should be taken within 45 minutes prior to the methylprednisolone infusion. In addition, vital signs should be obtained prior to the study drug or placebo infusion, then every 15 minutes (± 5 minutes) for the first hour; then every 30 minutes (± 10 minutes) until 1 hour after the end of the infusion. At non-infusion visits, the vital signs may be taken at any time during the visit.
- ^h **ECGs (pre- and postdose):** ECG should be performed within 45 minutes prior to the methylprednisolone infusion in all participants and within 60 minutes after completion of the ocrelizumab infusion. From OLE Week 72 onwards, ECG assessment is not mandatory; it should only be performed if clinically indicated.
- ⁱ **Telephone interview:** A structured **telephone interview** will be conducted by site personnel every 4 weeks *between visits* to identify and collect information on any changes in the participant's health status that warrant an unscheduled visit (including new or worsening neurological symptoms).
- ^j **MRI scans:** A brain MRI scan should be performed at the start of OLE phase if not done in the previous 12 weeks. In the OLE phase, brain MRIs should be done once a year. Brain MRI scans should occur within a window of ± 4 weeks of the scheduled visit. Also, brain MRI scans will be obtained in participants withdrawn from the OLE phase (at a withdrawal visit) if not performed during the previous 4 weeks.

- ^k **Antibody titers:** Measurement of antibody titers against common antigens (mumps, rubella, varicella, and *S. pneumoniae*) will be performed.
- ^l **HAHA:** In any case of anaphylaxis, anaphylactoid reaction, or serious or severe hypersensitivity reaction, HAHA and ocrelizumab concentration samples should be collected as close as possible to the event and then at 4 and 16 weeks postdose.
- PK samples:** In any case of anaphylaxis, anaphylactoid reaction, or serious or severe hypersensitivity reaction, HAHA and ocrelizumab concentration samples should be collected as close as possible to the event and then at 4 and 16 weeks postdose.

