^c After the first infusion, an evaluation will be performed before each subsequent infusion to ensure that the participant remains eligible for re-treatment (see Section 6.2.3).

^d Trial participants entering the study early will undergo more than 5 treatment cycles. When applicable, subsequent dosing cycles will consist of the same dosing regimen at 24-week intervals as Cycles 2–5.

^e The OLE phase for eligible participants begins after the primary database lock at the completion of the blinded treatment period. The OLE phase can terminate at any moment or cycle (see Section 4.1.9).

^f During the OLE phase, all participants will receive dual infusions of ocrelizumab 300 mg × 2 for the first cycle. For the subsequent cycles, participants will continue open-label treatment with a single infusion of 600 mg ocrelizumab IV every 24 weeks. For participants randomized to the ocrelizumab group, the first infusion of ocrelizumab in the OLE phase should respect a minimum of 20 weeks from last infusion in the blinded treatment period. For participants randomized to the placebo group, the first infusion of ocrelizumab in the OLE phase can occur once a participant meets the re-treatment criteria (see Section 6.2.3) at a scheduled visit following communication with the Sponsor.

Table 5 Overview of the Study Design and Dosing Regimen (cont.)

- ^g The safety follow-up period starts after the last 24-week treatment cycle has been completed (either during the blinded treatment period or the OLE phase). Participants who withdraw from treatment will also enter the safety follow-up period. The safety follow-up period will last *up to* 48 weeks following the last infusion. *Participants who start treatment with commercial ocrelizumab or another DMT will discontinue from the study completely and will not enter the safety follow-up period.*
- ^h A dose of 100 mg methylprednisolone IV and oral or IV antihistamine, such as diphenhydramine 50 mg or equivalent dose of alternative, will be administered prior to ocrelizumab or placebo infusions. In participants where methylprednisolone is contraindicated, equivalent doses of other IV steroids (e.g., dexamethasone) should be used as premedication.

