Magnetic resonance imaging is a useful tool for monitoring CNS lesions in MS. Different MRI-derived parameters have been related to clinical activity and T1-weighted Gd-enhancing lesions or new and/or enlarging hyperintense T2 lesions have been related to relapses. It is hypothesized that changes in brain volume may reflect brain atrophy as a result of MS-related tissue loss and may thereby correlate with long-term clinical outcome in these participants.

Brain MRI scans will be obtained in all participants at baseline and at Weeks 24, 48, and 120.

Scans will be performed by trained and certified MRI technicians. The following time windows apply:

- Visit 2 (baseline): after screening visit, but at least 10 days prior to the baseline visit
- Visit 5–17 (Weeks 24–120): should be performed within a window of ± 4 weeks of the scheduled visit
- In additional cycles during the blinded treatment period, an MRI should be performed annually
- In the OLE phase, MRI should be performed annually

If participants receive corticosteroids for an MS relapse, every effort should be made to obtain the scan prior to the first steroid dose if the pre-steroid scan is within 1 week of the scheduled visit. In participants receiving corticosteroids for an MS relapse, there should be an interval of 3 weeks between the last dose of corticosteroids and the scan.

The MRI will include the acquisition of scans at each timepoint with and/or without IV administered Gd contrast enhancement.

During the blinded treatment period, **MRI scans will be read by a centralized reading center for efficacy endpoints.** The centralized reading center is blinded to the treatment assignment and the reading is performed in the absence of clinical information. Further details on scanning acquisition sequences, methods, handling and transmission of the scans, certification of site MRI radiologist/technicians, and the procedures for the blinded analysis of the scans at the central reading center are described in a separate MRI technical manual.

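### New or enlarging T2 lesion counts are modelled by visit with no offset for accumulation time, so by-visit rates are not comparable across unequally spaced scans

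*SAP*

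**What the plan says.** SAP 4.5.3 covers two lesion counts: gadolinium-enhancing T1 lesions, and new or enlarging T2 lesions. It states: "For the combined ECP and OLE periods, these parameters will be analyzed by scheduled visit as follows". For post-baseline visits the model is: "Negative binomial model adjusted by Baseline T1 Gd Lesion (present or not) or Baseline T2 lesion count, Geographical Region (US vs. ROW) and Age". No offset or exposure time is listed. If the model does not converge, "unadjusted rate and exact poisson CI will be presented", with no denominator given for that rate.

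On scan timing, Protocol 5.11.2 states: "Brain MRI scans will be obtained in all participants at baseline and at Weeks 24, 48, and 120". For the extension, Protocol Table 4 (MRI footnote) adds: "A brain MRI scan should be performed at the start of OLE phase if not done in the previous 12 weeks"; scans are yearly after that. SAP 4.5.2.3 records that no scans took place between Week 120 and OLE start.

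Later in SAP 4.5.3, under annualized percentage change in MRI, the plan notes that "the time gap between 120 weeks and OLE start varies from patient to patient" and gives that as a reason to annualize. The formulas there are percent change or log change from the previous value. The measures named there, and the annualized rows in the SAP 4.2 output table, are brain, white-matter and cortical grey-matter volumes and T1 and T2 lesion volumes. In that table the lesion counts appear only by visit.

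**The concern.** A count of new or enlarging lesions accumulates over the time since its reference scan, so at an unchanged disease rate a longer interval gives a larger count. A model fitted visit by visit without a time term reports lesions per scan, and that quantity mixes lesion rate with interval length. The plan accepts this reasoning for volumes and uses patient-year denominators for adverse events (SAP 4.7.2), but does neither for these counts.

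The risk lies in reading along the row of visits. The by-visit display runs through the point where placebo patients switch to ocrelizumab, which is where a reader looks for a change. Part or all of any change seen there could come from the scan schedule. Gadolinium-enhancing lesions, if counted as those present on each scan, do not raise this problem.

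**Working it through.** The documents give no expected count, rate or power for this endpoint, so there is no planned figure to reproduce. The check is interval arithmetic.

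**Inputs**
- Blinded-period scans at Weeks 0, 24, 48 and 120 (Protocol 5.11.2), so intervals of 24, 24 and 72 weeks.
- OLE scans at OLE start and yearly. I take 48 weeks, because Protocol Table 4 marks OLE Weeks 0 and 48 and SAP 4.5.3 steps its relabelled MRI visits by 48 weeks.
- Scan window ±4 weeks (Protocol Table 1, MRI footnote).
- Last patient enrolled 27 December 2012 (SAP 4.5.4); OLE access from 12 October 2015 (SAP 1).
- Clinical cutoff 24 July 2015 (SAP 1), then about 3 + 6 months until patients have moved to the OLE (SAP 2), ending about 23 April 2016.
- The first-patient date is not given. Assumption: 12 to 18 months' accrual, as anticipated in Protocol 4.1.2.

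**Week 120 to OLE-start gap**
- Last patient: Week 120 falls on 16 April 2015. The gap is 25.6 weeks to 12 October 2015 and 53.3 weeks to 23 April 2016.
- First patient, 12-month accrual: 77.7 to 105.4 weeks.
- First patient, 18-month accrual: 103.9 to 131.6 weeks.
- Overall range: roughly 26 to 132 weeks.

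**If lesions are counted from the previous scan**

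Expected count = rate × interval. At a constant rate, the ratio of two visits is the ratio of their intervals.
- OLE Week 48 against Week 120: 48/72 = 0.67, an apparent 33% fall. With the ±4-week windows on the intervals, the ratio runs from 40/80 = 0.50 to 56/64 = 0.875.
- OLE Week 48 against Week 24 or Week 48: 48/24 = 2.0, an apparent doubling (40/32 = 1.25 to 56/16 = 3.5).
- OLE start against Week 120: 26/72 = 0.36 to 132/72 = 1.83.
- OLE Week 48 against OLE start: 48/26 = 1.85 down to 48/132 = 0.36. It is a rise for gaps under 48 weeks and a fall for gaps over 48 weeks.

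A simulation illustrates this (20,000 patients; assumed 1 lesion per 48 weeks, dispersion 1, gap uniform on 26 to 131 weeks):

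| Scan | Mean per scan | Per 48 weeks, time-adjusted |
|---|---|---|
| Week 24 | 0.50 | 1.00 |
| Week 48 | 0.49 | 0.99 |
| Week 120 | 1.50 | 1.00 |
| OLE start | 1.62 | 0.99 |
| OLE Week 48 | 0.99 | 0.99 |
| OLE Week 96 | 1.00 | 1.00 |

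**If lesions are counted from baseline**

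Accumulation times are 24, 48 and 120 weeks, then 120 + 26 = 146 to 120 + 132 = 252 weeks at OLE start. At a constant rate the OLE-start count is 146/120 = 1.22 to 252/120 = 2.10 times the Week 120 count. Counts rise with time, and no fall appears.

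**Arm comparison within a visit**

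With a simulated true ratio of 0.20 and the same intervals in both arms, the fitted ratio was 0.199 with and without the offset at Week 120, and 0.200 both ways at a variable OLE-start gap.

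**Relabelled visits**

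SAP 4.5.3 assigns OLE scans before Week 168 to Week 168, and the rest to the nearest 48-week label within ±24 weeks. If that rule also covers counts, the Week 216 label (Weeks 192 to 240) would hold OLE-start scans after gaps of 72 to 120 weeks together with 48-week OLE scans. A patient with a 26-week gap, for example, has the OLE Week 48 scan at study Week 120 + 26 + 48 = 194.

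**The case against.** The strongest reply is that no planned comparison is shown to be invalid. Each visit is modelled separately, the endpoint is exploratory and outside the SAP 4.5.2 hierarchy, and at Weeks 24, 48 and 120 the arms share the same nominal intervals. That stands. The weakness is in comparison across visits, which the plan displays but does not test. It is also fair that the SAP is silent on an offset and does not rule one out, and that reading procedures sit in a separate MRI technical manual. Still, the listed model terms and the undefined fallback rate leave a programmer with nothing that brings time in.

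Three stronger readings are tempting, and the documents do not support them.

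- *A fall in every group after the switch to open-label drug.* This needs counting from the previous scan, which neither document states, and a gap longer than 48 weeks, which not every patient has. The relabelling, if it applies to counts, would change which visits differ.
- *A definite size for the fall from OLE start to OLE Week 48.* Uniform accrual over 12 or 18 months and uniform OLE entry over 6 months give mean gaps of 0.49 + 0.50 + 0.25 = 1.24 and 0.49 + 0.75 + 0.25 = 1.49 years. Against 48 weeks (0.92 year), the falls are 1 − 0.92/1.24 = 26% and 1 − 0.92/1.49 = 38%. SAP 2.2 and 3.1 report a late screening boost, so uniform accrual is doubtful. Linearly rising accrual gives means of 1.07 and 1.24 years and falls of 14% and 26%. The figure follows the assumption.
- *A bias between arms at OLE start.* Protocol Table 5 (footnote f) says of ocrelizumab patients only that "the first infusion of ocrelizumab in the OLE phase should respect a minimum of 20 weeks from last infusion in the blinded treatment period"; placebo patients may start at a scheduled visit once they meet the re-treatment criteria. Entry timing could therefore differ by arm, and a longer ocrelizumab interval would raise ocrelizumab counts, against the drug. The documents give no actual waiting times, so this is possible but cannot be quantified.

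**Conclusion.** The point holds as a matter of comparability across visits. Followed as written, SAP 4.5.3 yields per-scan lesion counts over intervals of 24, 24, 72, roughly 26 to 132, and about 48 weeks, with no adjustment for time. The volume measures are adjusted for this reason.

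The firmest figure is the 33% apparent fall from Week 120 to OLE Week 48. It assumes counting from the previous scan, a constant rate and 48-week OLE spacing, and needs no accrual assumption. On the same basis there is an apparent doubling against Week 24 or 48, and a change in either direction against OLE start. Counting from baseline gives a rise instead. The upper end of the gap range depends on assumed accrual.

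Randomized contrasts at Weeks 24, 48 and 120 are essentially unaffected. Severity is low: this is an inexpensive improvement to an exploratory endpoint.

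**What to change.** In SAP 4.5.3, for new or enlarging T2 lesions only:

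1. Name the scan against which a lesion is judged new or enlarging (previous scan or baseline).
2. Add log(time since that reference scan) as an offset in the negative binomial model, and report annualized rates by visit and arm.
3. Use person-time since the reference scan as the denominator of the fallback Poisson rate.
4. Say whether the MRI visit relabelling under annualized change also applies to lesion counts.

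Leave the gadolinium-enhancing lesion model unchanged.

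Two texts should be reconciled at the same time. The SAP 4.2 table calls the T2 lesions new and enhancing, where SAP 4.5.3 has new or enlarging. Protocol 5.11.2 and Table 2 provide for annual MRI after Week 120 in the blinded period, whereas SAP 4.5.2.3 says none was done before OLE start; any such scans would shorten the gap.

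The cost is one model term and a few sentences. The annualized-change formulas in SAP 4.5.3 already use the dates of the MRI visits, so no new data are needed.

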Participants who fulfill the eligibility criteria outlined in the following inclusion and exclusion sections of this substudy protocol can be enrolled into the study.

INCLUSION CRITERIA

Participants must meet the following criteria to be eligible for substudy entry:

- Having received at least 1 dose (2 infusions separated by 2 weeks) of blinded study drug (either placebo or ocrelizumab) in the blinded treatment period of Study WA25046
- Having withdrawn early from treatment during the blinded treatment period of Study WA25046 for any reason, with the exception of those participants who discontinued due to hypersensitivity to ocrelizumab if it manifested as a Grade 4 IRR; both participants who entered the safety follow-up and participants who withdrew from study are eligible
- Participants whose EDSS at screening is > 6.5 are eligible if in the judgment of the investigator and following discussion with the participant, the benefit–risk of ocrelizumab treatment is considered acceptable
- Willing to use appropriate contraceptive methods as described in Section 5.4 of the main protocol
- Ability to provide written informed consent and to be able to follow the schedule of activities of the substudy

EXCLUSION CRITERIA

Participants who at the time of screening for substudy entry meet any of the following criteria will not be allowed to enter the substudy:

Exclusions Inherited from the Blinded Treatment Period of WA25046

- Meeting any of the general exclusion criteria of the blinded treatment phase listed in Section 5.3 of the main protocol

Appendix 8 Open-Label Extension Substudy in Participants Who Discontinued Treatment in the Blinded Phase of Study WA25046 (cont.)

- Meeting any of the 'exclusion criteria related to general health' listed in Section 5.3.1 of the main protocol
- Meeting any of the 'exclusion criteria related to medications' listed in Section 5.3.2 of the main protocol

Exclusions Related to Laboratory Findings

- Positive serum β human chorionic gonadotropin (β -hCG) measured at screening
- Positive screening tests for hepatitis B (hepatitis B surface antigen [HBsAg] positive, or positive total hepatitis B core antibody [HBcAb] confirmed by a positive viral DNA polymerase chain reaction [PCR]) or hepatitis C virus antibody (HepCAb; see Section 5.13.1.1)
- Positive rapid plasma reagin (RPR) if confirmed by microhemagglutination assay (MHA-TP) or fluorescent treponemal antibody absorption (FTA-ABS) test
- CD4 count $<250/\mu\text{L}$

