4.1.2 OLE ITT Population

All patients receiving at least one dose of OLE as part of the OLE will be included in the OLE ITT population. Patients will be summarized according to their randomized treatment.

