4.2 OVERVIEW OF ANALYSES PLANNED FOR THE EXTENSION PERIODS

Overview of outcome measures and analyses performed for the extension periods in addition to the analyses performed for the primary CSR:

Period (Population) / Analyses	Extended controlled (ITT)	OLE (OLE ITT)	Combined extension (ITT)
Study conduct Patient Disposition (All patients)			X
Treatment group comparability Summary of demographics		X	
Baseline Disease Characteristics & baseline MRI Assessments		X	
Exposure to study drug Exposure to Ocrelizumab/Placebo			X
Confirmed disability progression /EDSS/T25-FW/9-HPT Time to Onset of Confirmed Disability Progression for at Least 12 weeks	X	X	X
Time to Onset of Confirmed Disability Progression for at Least 24 weeks	X	X	X

Period (Population) / Analyses	Extended controlled (ITT)	OLE (OLE ITT)	Combined extension (ITT)
Time to composite confirmed disability progression (EDSS or T25-FW or 9-HPT) for at Least 12 weeks	X	X	X
Time to composite confirmed disability progression (EDSS or T25-FW or 9-HPT) for at Least 24 weeks	X	X	X
Time to Onset of Confirmed Disability Progression Confirmed for ≥ 48 weeks	X	X	X
Time to composite confirmed disability progression for at least 48 weeks	X	X	X
Time to Onset of Confirmed EDSS ≥ 7 for at least 24 weeks	X	X	X
Time to Onset of Confirmed EDSS ≥ 7 for at least 48 weeks	X	X	X
Time to confirmed 20% increase in T25-FW for at least 12 weeks	X	X	X
Time to confirmed 20% increase in T25-FW for at least 24 weeks	X	X	X
Time to confirmed 20% increase in T25-FW for at least 48 weeks	X	X	X
Time to confirmed 20% increase in 9-Hole Peg for at least 12 weeks	X	X	X
Time to confirmed 20% increase in 9-Hole Peg for at least 24 weeks	X	X	X
Time to confirmed 20% increase in 9-Hole Peg for at least 48 weeks	X	X	X
Change in T25-FW speed from baseline (MMRM)	X	X	X
Change in EDSS from baseline (MMRM)	X	X	X
Change in MSFCS from baseline (MMRM)	X	X	X
MRI measures		X	
Ratio and percent change in T2 lesion volume from baseline		X	X
Ratio and percent change in non-enhancing T1 lesion volume from baseline		X	X
Number of Gadolinium-enhancing T1 lesions by visit			X
Number of new and enhancing T2 hyperintense lesions by visit			X
Percent change in total brain volume from Baseline		X	X
Percent change in total brain volume from Week 24			X
Percent change in cortical gray matter volume from Baseline		X	X

Period (Population) / Analyses	Extended controlled (ITT)	OLE (OLE ITT)	Combined extension (ITT)

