- For OLE, demography and stratification factors, baseline disease characteristics, MS disease history and baseline MRI data will be summarized using the information collected at OLE baseline as described in the previous section, but subsetting for the OLE ITT population.
- OLE baseline score (EDSS, MRI, etc.) is the latest score collected prior to (including) OLE 1st Dose and after (including) Week 120. If the patient had no measurements within the defined time window, then set the OLE baseline score to be missing.

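### The OLE-only time to confirmed EDSS ≥ 7 does not require a score below 7 at OLE baseline, so patients who enter the OLE at 7 or above and stay there would be counted as OLE onsets

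*SAP*

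**What the plan says.** SAP 4.5.3 takes an EDSS of 7 or more, which it equates with needing a wheelchair, "to be defined as a disability progression event that is sustained for at least 24 or 48 weeks". For everything else it refers back: "The analysis will be conducted as described for the primary analysis". For the OLE alone it adds "Analysis containing only data from OLE will be performed considering the OLE baseline".

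In the SAP 4.2 overview table, the row "Time to Onset of Confirmed EDSS ≥ 7 for at least 24 weeks" and its 48-week counterpart are marked in all three period columns, including the OLE column headed by the OLE ITT population. SAP 4.1.2 defines that population: "All patients receiving at least one dose of OLE as part of the OLE will be included in the OLE ITT population". It carries no EDSS condition. SAP 4.4 gives the baseline: "OLE baseline score (EDSS, MRI, etc.) is the latest score collected prior to (including) OLE 1st Dose and after (including) Week 120". The score is set to missing if nothing falls in that window.

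The closing text of SAP 4.2 says that extension analyses follow the primary rules unless an exception is written, and none is written for this endpoint. The only OLE-specific event rule, in the extension paragraph of SAP 4.5.1, is that the initial progression must occur on OLE treatment.

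**The concern.** A time-to-onset analysis should start with patients who have not yet had the event. Here the event is a level on the scale, and nothing in the rules removes patients who already have that level when the OLE clock starts. A patient who needed a wheelchair before the OLE and still needs one would add to the OLE curve as though the milestone had been reached during the OLE.

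Two things are at stake. First, the OLE curves would overstate new onsets in both arms. Second, if more ex-placebo than ocrelizumab patients are at 7 or above at OLE entry, a difference that arose in the blinded period would reappear as a difference arising in the OLE. Requiring a wheelchair is a milestone that readers will take at face value.

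**Working it through.** The plan states no figure for this endpoint, so there is none to reproduce.

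**1. Why re-baselining works elsewhere but not here.** The instruction to use the OLE baseline is shared with the confirmed disability progression endpoints.
- For those endpoints the event is a rise. A patient at 7.0 at OLE baseline needs at least 7.5, so the new baseline resets the event.
- For EDSS ≥ 7 the threshold does not move. A patient at 7.0 at OLE baseline already satisfies it, and the new baseline only resets the time origin.

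**2. Whether such patients can exist in the main OLE.** The 3.0–6.5 limit in Protocol 5.2 applies at screening. OLE eligibility in Protocol 5.4 lists no EDSS ceiling. Protocol 4.1.5.2 does not force patients with confirmed progression off blinded treatment. They are therefore possible, but the documents give no count.

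**3. What happens to one of them.** Protocol Table 4 has EDSS on OLE Day 1 and at Week 12. A patient still at 7.0 supplies an initial event by Week 12. It counts once the score has held for 24 or 48 weeks, with every score in between qualifying.

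**4. Illustrative size.** All inputs are assumptions: p is the share at ≥ 7 at OLE baseline, true OLE incidence is 15% in both arms, and every prevalent case is confirmed.

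Counted proportion = p + (1 − p) × 0.15. Prevalent share of counted events = p ÷ counted proportion.

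| p, ex-placebo / ocrelizumab | Counted, ex-placebo | Counted, ocrelizumab | Ratio | Prevalent share of counted events |
|---|---|---|---|---|
| 3% / 3% | 0.03 + 0.97 × 0.15 = 0.1755 | 0.1755 | 1.00 | 17% / 17% |
| 5% / 3% | 0.05 + 0.95 × 0.15 = 0.1925 | 0.1755 | 1.10 | 26% / 17% |
| 10% / 6% | 0.10 + 0.90 × 0.15 = 0.235 | 0.06 + 0.94 × 0.15 = 0.201 | 1.17 | 43% / 30% |

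With equal prevalence the contrast is null, but 0.1755 is reported where the true onset proportion is 0.15.

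**5. On the hazard ratio scale.** The planned estimate is a Cox hazard ratio, so a simulation was also run. It assumed five years of OLE, 12-weekly visits, 2:1 arms, 10–20% new onset over five years with no arm difference, and 80–100% of prevalent patients staying at ≥ 7. The hazard ratio (ocrelizumab versus ex-placebo) was 0.98–1.06 for 3% / 3%, 0.88–0.94 for 5% / 3%, and 0.78–0.89 for 10% / 6%. Restricting to patients below 7 gave 0.92–1.08 across all settings, which is noise around the assumed null. That noise overlaps the 5% / 3% result, so these figures show direction more than size.

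**The case against.** **Onset may already imply a risk set.** The endpoint is named time to onset, and the primary method measures time to the first progression. On that reading a patient already at 7 is not at risk. The SAP never says outright that such patients count, and the programs may have filtered them. This stands as a caution about what was actually run. It does not settle the text: the event rule, the population and the on-treatment rule, followed literally, do count them.

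**Confirmation is required.** The first OLE visit gives only an initial event, and patients who drop below 7 before confirmation do not count. This stands, which is why the table's assumption of full confirmation is an upper case.

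**Appendix 8.** A reader might point to Protocol Appendix 8, where "Participants whose EDSS at screening is > 6.5 are eligible if in the judgment of the investigator", as proof that high scores enter this analysis. It is not. That substudy is for patients who left blinded treatment early, and its background section says their data are to be analyzed separately. The OLE ITT definition does not mention them. The point rests on the main OLE alone.

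**Inference about direction.** A reader might also infer that, because Appendix 8 reports that the blinded period met its primary endpoint, the OLE-only result must favor ocrelizumab spuriously. The documents do not support that. The primary endpoint is 12-week confirmed progression, and no share at ≥ 7 at OLE entry is given for either arm. An imbalance is plausible but not shown.

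**Low consequence.** This is one period of an exploratory endpoint outside the hierarchy. OLE baseline EDSS will be summarized under SAP 4.4, so a shift between arms could be seen, though not the number at ≥ 7. This stands and limits the weight of the point.

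**Conclusion.** The point holds for the SAP as written. In the OLE-only analysis, main-OLE patients already at EDSS ≥ 7 who remain there through confirmation meet every stated condition for an OLE onset. The size cannot be known from the documents. Under the assumptions above, equal prevalence distorts the curves but not the contrast, while 5% versus 3% or 10% versus 6% gives a ratio of counted proportions of about 1.10 or 1.17 with no true OLE difference.

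The primary endpoint and the secondary hierarchy are untouched. The extended controlled and combined-period versions of this endpoint are essentially free of the problem, because they start from study baseline in patients screened at 6.5 or below. The change is worth making because it is cheap and the milestone is easily misread, not because any trial conclusion depends on it.

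**What to change.** Add to SAP 4.5.3:

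> For the OLE-only EDSS ≥ 7 analyses, the risk set is OLE ITT patients with a non-missing OLE baseline EDSS < 7; patients at ≥ 7 and patients with missing OLE baseline are excluded and tabulated by randomized arm.

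The cost is one sentence, one filter and one small table. SAP 4.4 already defines the baseline and when it is missing, so no new data are needed.

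The drawback is a somewhat smaller risk set that is selected on a score measured after randomization. The filter does not make the OLE-only contrast a randomized one. Blinded-period differences below the threshold, such as more patients sitting at 6.5 in one arm, could still carry over. The SAP should therefore keep the combined extended controlled and OLE analysis from study baseline as the main between-arm comparison for this endpoint, and present the OLE-only version as descriptive.
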